9.1.1 Statement of Treatment Aim and Rationale

Treatment rationale is to provide long-term local and distant disease control by treating limited oligometastatic renal cancer (1-5 isolated metastases) with a single fraction of stereotactic ablative radiotherapy in conjunction with pembrolizumab.

9.1.2 Treatment Schedule

Radiation therapy should commence within 4 weeks of patient registration on the study. A single dose of 20 Gy should be prescribed, although a single 18Gy fraction can be used as an alternative for a centrally located lung lesion or a spinal lesion with a SINS score of ≥ 7 after review at SABR chart round. Typically a single fraction of 20Gy should be prescribed for spinal vertebral lesions, however, for those with a SINS score of ≥ 7 after review at SABR chart round, a single 18Gy fraction is preferred.

9.1.3 Procedures if SABR is not Technically Deliverable

If after evaluation of a tumour location and treatment plan dosimetry, SABR is not technically or safely possible to deliver, a conventional hypofractionated course of radiotherapy of 30Gy in 10 fractions or 36Gy in 12 fractions should be delivered (total dose selected at clinician discretion). In this scenario, delivery of SABR to other sites of disease should be scheduled towards the end of, or immediately after, the course of conventional radiotherapy.

9.1.4 Planning Simulation

Simulation procedures will vary according to treatment site. These procedures are in accordance with the Royal Australian and New Zealand College of Radiologists (RANZCR) SABR guidelines (Foote, M. et al., J Med Imaging Radiat Oncol, 2015. **59**(5): p. 646-53).

9.1.5 Patient Positioning

Patients will be positioned supine in a manner which isolates the region for treatment from surrounding anatomy where possible e.g. arms above the head for thoracic targets. The final treatment position used will be determined based on the clinical judgement of the treating Radiation Therapy team. The underlying principle that should always be observed is that the patient position must ensure an appropriately stable position that is both reproducible and able to be tolerated by the patient for the anticipated length of planning and treatment delivery procedures.

9.1.6 Reference Points/Tattoos

In room lasers will be used to setup and align the patient into the correct position.

In order to facilitate the pre-treatment setup, skin tattoos will be placed at the following locations:

1. Anteriorly at the anticipated isocentre location on an appropriately stable anatomical point.
2. Laterally at the level of the anticipated isocentre position to facilitate reproduction of patient rotation.
3. At an appropriate distance (typically 15-20cm) superior or inferior to the isocentre position to facilitate midline alignment.

Variation to the above described tattoo locations is permitted at the judgement of the planning radiation therapy team to optimise reproduction of patient position, provided there is clear documentation of the change. The position of skin tattoos will be documented in the radiation oncology management system, and photographs taken to facilitate identification of relevant tattoos by the treating radiation therapists.

9.1.7 Immobilisation

Effective immobilisation customised to the treatment site is essential to ensure reproducibility of patient position. A high quality customised vaclock style device capable of indexation to the treatment couch is required. The vaclock bag device must adequately encompass the treatment volume and an appropriate area beyond to permit reproducibility of the target and surrounding anatomy.

The actual design of the immobilisation will depend on the treatment site. When deciding on immobilisation consideration must be given to:

- Patient comfort as the treatment time can exceed 45 minutes in particular if more than one lesion is to be treated in a single session.
- The possible need to immobilise more than one lesion at the same time.
- Motion management (see section 9.1.9).
- Reproducibility between planning, mock-up and treatment.
- Image guidance as the field of view of CBCT is limited and patient shifts between imaging and treatment should be avoided.

9.1.8 Planning Imaging

A planning CT scan with patient in the treatment position will be used for treatment planning. The CT must be of 3mm slice spacing and width or less. In order to allow placement of non-coplanar beams through valid body contours, the CT scan length should extend as a minimum ten centimetres superior and inferior to the intended treatment volume. CT scan length should also include the entire volume of any organ at risk for which a volumetric dose constraint is set.

9.1.9 Consideration of Motion

Motion must be considered in the planning stage for lesions that may be affected by breathing motion. For target volumes in the abdomino-thoracic region, consideration of organ motion should be made as part of the radiotherapy plan when necessary. In such cases, a 4-dimensional CT scan will be acquired for planning. The internal target volume (ITV) concept developed by the International Commission on Radiation Units and measurements will be used for target delineation. An ITV is developed by combining all positions of the target across the respiratory cycle.

For target volumes outside of the abdomino-thoracic region not participant to respiratory excursion, a three-dimensional planning CT scan is adequate.

Gated delivery would only be considered in extreme cases where the lesion moves more than 1 cm.

9.1.10 Pre-Treatment Mock-up (only if required)

When deemed as required, a patient will be asked to attend a mock-up session on the Linear accelerator prior to the treatment delivery appointment. The purpose of the mock-up is two-fold:

- To test adequate visualisation of the target and surrounding anatomy with use of the proposed verification imaging.
- To test physical clearance of beam angles.

When a pre-treatment mock-up is required, the patient will be positioned in the treatment position and the beam isocentre set. Verification imaging will be acquired, and assessed online to ensure adequate target visualisation. All beam angles will be set to ensure deliverability on the Linear accelerator.

9.1.11 Target Volume Definitions/Field Borders

Target Volumes

Target Volumes must be defined as per ICRU 50, 62, and 83 with clear definitions, individual contouring and standardised labelling [83-85]. These include:

- Gross Tumour Volume (GTV)
- Internal Target Volume – The Internal Target Volume (ITV) is a concept developed by the International Commission on Radiation Units and Measurements (ICRU1999)[86] and will be used for lesions that move or are likely to change their shape during treatment. The ITV takes into account the total tumour excursion through respiration. It is a Boolean combination of all locations that would be occupied by the target at any phase of the breathing cycle.
- Planning Target Volume (PTV) – ITV to PTV margins must take into consideration setup uncertainties. A PTV expansion of 5mm global expansion in the axial and craniocaudal directions is required as a minimum. For locations that do not require a 4D CT for motion management – $PTV = GTV + 5mm$

For contouring of bone metastases all available imaging will be taken into account.

For contouring of spinal bone metastases international consensus guidelines (Appendix 4) will be followed.

Field Borders

Conformal field shaping must be performed using a multileaf collimator device with central leaf width of 5mm or less projected to isocentre. The margin between the target volume and the field edge is typically expected to be 0- 2mm in the axial direction, however individual beams eye views may be optimized based on the resultant dose distribution to maximise conformity of the prescription isodose to the PTV. Negative margins from field edge to target volume may also be employed to achieve greater conformity. In order to achieve coverage of the planning target volume with the prescription isodose, it may be necessary to accept a larger than 0-2mm margin from the target volume to the MLC defined field edge, particularly in the craniocaudal axis.

9.1.12 Dose Prescription and Fractionation

Dose is prescribed to the covering isodose of the PTV. For plan optimisation, a minimum of $D_{99}=100\%$ of the prescription isodose will be accepted except for treatment of the spine. However, a target coverage of $D_{95}=100\%$ is acceptable if required to respect an organ-at-risk dose tolerance. Within the spine, in the case of no previous radiotherapy a D_{90} of $> 90\%$ (prescription dose) is ideal, however a D_{90} of $> 80\%$ (prescription dose) is acceptable. In particular for small lesions treated using 3D conformal beam arrangements a large dose inhomogeneity can be expected with the maximum dose far exceeding the prescription dose. During the optimisation process, the PTV max dose should typically aim to achieve a D_{Max} of 125%. This is common in stereotactic treatments and effectively aims for a prescription to the 80% isodose (covering isodose) when normalised to the PTV max. Prescription to lower isodose ranges (between 70 to 80%) is acceptable, particularly for smaller targets.

Maximum dose and dose to the ICRU reference point (centred on the CTV/ITV) should be reported.

The use of IMRT/VMAT in general will make target dose more homogeneous. Care must be taken to not allow any cold spots in the ITV/GTV when using IMRT/VMAT. Phantom volumes with the PTV can be used as planning objectives during plan optimisation to enable desired dose inhomogeneity.

9.1.13 Treatment Duration

Wherever possible, all target metastases to be treated with SABR should be treated on the same day for patient convenience. If this is not possible for practical or logistical reasons all lesions will be treated within 21 calendar days.

9.1.14 Normal Tissue Contouring and Dose Constraints

Targets in the head and neck region, or in the mediastinum should not be treated with SABR. Targets should generally be located > 1cm from any hollow gastrointestinal luminal structure or major nervous plexus.

Table 4: Normal Tissue Contouring and Dose Constraints

Organ	Contouring	Parameter	Dose-Volume Constraints
Kidney	Entire kidney	V10	33%
Spinal planning risk volume (PRV)	Spinal Cord + 3mm expansion or Thecal Sac (1cm above and below target)*	Maximum dose	0.03cc ≤ 12Gy
Brain Stem	Including midbrain, pons and medulla	Maximum Dose	0.03cc < 12.5Gy
Skin (5mm subcutis)	Body surface – 5mm	Maximum Dose	0.03cc ≤ 24Gy
Small Bowel	All small bowel contoured 5cm above and below PTV	Maximum Dose/ Volume	30cc ≤ 12.5Gy
		Maximum Dose	0.03cc ≤ 20 Gy
Stomach	Entire Stomach	Maximum Dose	0.03cc < 20Gy
Liver	Entire liver	Maximum Dose/ Volume	700cc ≤ 15Gy
Lung	Combined Left and right Lung - GTV	Maximum Dose/ Volume	1000cc ≤ 7.4Gy
Oesophagus	Cricoid to gastro-oesophageal junction	Maximum Dose	0.03cc ≤ 15.4Gy
Rectum	Recto-sigmoid to anal canal (solid structure)	Maximum Dose/ Volume	20 cc ≤ 14.3Gy
Bladder wall	Entire structure	Maximum Dose/ Volume	15 cc ≤ 11.4Gy
Heart / Pericardium	Entire Structure	Maximum Dose/ Volume	15 cc ≤ 16Gy
Brachial Plexus	Including nerve roots	Maximum Dose	0.03 cc ≤ 15.4Gy

Dose constraints have been informed by QUANTEC recommendation guidelines (Table 4), completed RTOG protocols, and the AAPM TG101 [87] working party consensus guidelines.

* Where an MRI is not feasible or thecal sac/spinal cord cannot be clearly delineated, spinal canal may be used to define spinal PRV.

Note: Maximum dose is defined to a point. The minimum meaningful volume for a point is 0.035 cc.

When planning more than one lesion a summary plan must be created. The dose constraints apply to the summary plan.

SPINAL CANAL: QUANTEC summary [88] recommendations for maximum dose for a single fraction is a Dmax of 13Gy, and in 3 fractions is 20Gy. Limits for our technique are more conservative at 12Gy for a single fraction SBRT. This is also lower than the AAPM consensus recommendation of a max point dose of 14Gy [87]. In instances where the spinal cord has received previous radiotherapy, the spine should be re-imaged using an MRI or other appropriate investigations to check for radiation myelopathy/spinal necrosis if neurological symptoms are present.

BRAINSTEM: QUANTEC summary [89] recommends that for single fraction stereotactic radiosurgery a maximum brainstem dose of 12.5Gy is associated with a low risk of toxicity. They also note that higher doses (15-20Gy) have been used with low reported incidence of complications in patient groups with poor prognosis for long term survival (e.g brainstem metastases [90, 91]). We have used the lower recommended limit of 12.5Gy.

SKIN: National Comprehensive Cancer Network (NCCN) consensus guideline recommendations are that dose to skin should be limited to 26Gy for a single fraction and 30Gy in 3 fractions. Limits for our technique are more conservative than this at 24Gy for a single fraction

SMALL BOWEL: QUANTEC summary [92] recommendations are that dose circumferentially covering any volume of small bowel should not be > 12.5Gy in a single fraction. The maximum point dose recommendation for a 3-fraction approach is <30Gy. This 30Gy recommendation concurs with the seminal phase I/II study reported by Rusthoven et al.[39]. As an alternative, The University of Wurzburg constrains the dose to half the circumference of small bowel, which should not receive more than the prescription dose during SBRT [personal correspondence].

STOMACH: QUANTEC summary [92] recommendations are that a maximum point dose should be <30Gy in 3 fraction SBRT. The volume receiving >22.5Gy should be < 5cc.

LIVER: QUANTEC summary [93] recommendations are that ≤ 700mL of normal liver receives ≤15Gy in SBRT. University of Wurzburg do not use a dose constraint for single fraction radiosurgery of 30Gy in liver targets [[name], personal communication]. As the proportion of irradiated liver will be considerably smaller during SABR for bone or lymph node metastases than in radiosurgery of the liver, it is reasonable not to apply a liver dose constraint to the single fraction cohort receiving 20Gy.

LARGE VESSELS: Conventional radiotherapy is known to cause late fibrosis and injury to small and large vessels, usually many years after the initial irradiation. In the context of SABR treatment, it is important to note that despite the pancreas' proximity to major vessels such as the superior mesenteric vessels and abdominal aorta, no toxicities secondary to large vessel injury have been reported secondary to SBRT. Similarly in the liver, no clinically relevant large vessel effects have been reported secondary to irradiation of the inferior vena cava. This may

be in part due to the patient population, who typically are medically inoperable and have life-spans limited by other medical comorbidities. To the study team's knowledge, clinically significant large vessel injuries have been reported only in the context of combined surgery and radiation, or re-irradiation using SBRT of significantly higher doses than is allowable in the context of this study. Doses should be limited to the large vessels following ALARA principles.

OESOPHAGUS: Based on recommendations from AAPM Task Group 101 consensus recommendations [87], circumferential irradiation of oesophagus is not allowed.

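### Section 9.1.14 sets a liver dose limit in Table 4, then permits none at 20 Gy in a single fraction, and does not say which rule governs a liver target

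*Combined protocol and SAP*

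**What the plan says.** All the conflicting text is in section 9.1.14.

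- **Table 4, liver row.** The entire liver is contoured, with a dose-volume limit of 700 cc and 15 Gy. The row has no footnote and no exemption by dose, cohort or target site. For patients with more than one lesion the section requires a summed plan and adds: "The dose constraints apply to the summary plan".
- **Liver note.** It reports a published recommendation, printed with a ≤ sign before the words "700mL of normal liver receives ≤15Gy in SBRT". It then cites an outside centre that sets no constraint for single-fraction 30 Gy treatment of liver targets. Finally it reasons that the irradiated share of liver will be "considerably smaller during SABR for bone or lymph node metastases than in radiosurgery of the liver", and concludes that "it is reasonable not to apply a liver dose constraint to the single fraction cohort receiving 20Gy".
- **Sites barred from SABR.** "Targets in the head and neck region, or in the mediastinum should not be treated with SABR". The liver is not named.

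Other sections fix the scope. Section 9.1 makes all SABR a single fraction. Section 9.1.2 makes 20 Gy the default, with 18 Gy as an alternative only for a central lung lesion or a spinal lesion with a SINS score of 7 or more. Table 3 in section 8.3 gives a separate AST/ALT threshold for patients with liver metastases, so they are eligible. Section 11.2.6 anticipates inflammation in liver tissue after SABR.

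**The concern.** A planner with a liver target finds a limit in the table and, in the accompanying note, a permission to apply none. Both can be defended from the text, so two sites could plan the same patient differently and each claim to follow the protocol.

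The answer has a practical consequence. Section 9.1 allows target coverage to fall from D99=100% to D95=100% when an organ-at-risk tolerance requires it. A planner therefore has to know whether the liver has a tolerance in this trial.

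Safety is the primary objective (section 6.2). A combined liver enzyme and bilirubin elevation is one of the two events of clinical interest (section 10.8.5.3), and Table 6 generally ends pembrolizumab for grade 3-4 AST, ALT or bilirubin elevation. The event-count stopping criteria in section 11.2.10 cover only pneumonitis and bowel toxicity. If the liver limit is applied in some plans and not in others, a hepatic event is harder to attribute to radiotherapy or drug.

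**Working it through.** **Step 1: does the waiver reach a liver target?** All SABR is one fraction and the dose is 20 Gy unless the lesion is central lung or qualifying spine. A liver target is neither, so it receives 20 Gy in one fraction. The protocol has no multi-fraction SABR cohort, so the words about a single-fraction cohort narrow nothing. Taken literally, the waiver covers a liver target.

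**Step 2: does the reasoning reach a liver target?** The stated reason is that bone and nodal treatments irradiate less liver than liver radiosurgery does. That reason fails when the target is in the liver. The preceding sentence, on an outside centre's liver targets, points the other way. The scope cannot be settled from the text.

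**Step 3: how do the other organ notes behave?** Three of them state the trial's own limit, and each repeats its Table 4 row:

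- spinal canal, 12 Gy: "Limits for our technique are more conservative at 12Gy for a single fraction SBRT"
- brainstem, 12.5 Gy: "We have used the lower recommended limit of 12.5Gy"
- skin, 24 Gy: "Limits for our technique are more conservative than this at 24Gy for a single fraction"

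Only the liver note sets its row aside, and no rule of precedence appears in the section or in the dose, prescription and eligibility sections.

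**Step 4: when would the limit matter?** The plan gives no figure for this, so the bounds below are derived.

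Inputs from the protocol: 20 Gy prescription (9.1.2); D99=100% coverage (9.1); an aim that the 50% isodose volume is at most 5 times the target volume (CI50, 9.1.15.7); the 700 cc and 15 Gy figures (Table 4).

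Assumptions not in the protocol: one spherical planning target volume (PTV) wholly within the liver; liver volume L from 1000 to 2000 cc; isodose percentages taken relative to the prescribed 20 Gy.

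The 50% isodose is 0.5 × 20 = 10 Gy. Writing Vx for the volume receiving at least x Gy, V15 ≤ V10 ≤ 5 × PTV. If percentages were instead relative to a maximum of 143% of prescription, the 50% line would be 0.5 × 1.43 × 20 = 14.3 Gy. That is still below 15 Gy, so the bound holds.

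The row can be read two ways:

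- Spared reading, at least 700 cc at ≤15 Gy: V15 ≤ L − 700. No breach is possible if PTV < (L − 700)/5.
- Exposed reading, at most 700 cc above 15 Gy: V15 ≤ 700. No breach is possible if PTV < 700/5 = 140 cc.

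Sphere diameter = (6 × volume/π)^(1/3).

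| L (cc) | L − 700 (cc) | Spared: no breach below | Exposed: no breach below |
|---|---|---|---|
| 1000 | 300 | 60 cc (4.9 cm) | 140 cc (6.4 cm) |
| 1500 | 800 | 160 cc (6.7 cm) | 140 cc (6.4 cm) |
| 2000 | 1300 | 260 cc (7.9 cm) | 140 cc (6.4 cm) |

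The smallest threshold over this range, under either reading, is 60 cc. A single 4 cm PTV is 33.5 cc, so at most 5 × 33.5 = 168 cc exceeds 15 Gy. It passes both readings at every liver volume shown.

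The limit is not empty. With D99=100%, V15 ≥ 0.99 × PTV. In a 1000 cc liver under the spared reading it must be breached once PTV exceeds 300/0.99 = 303 cc (8.3 cm).

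The two readings allow the same exposed volume when L − 700 = 700, that is L = 1400 cc. Below that the spared reading is stricter; above it the exposed reading is.

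For several liver targets no threshold is claimed. Doses add, and section 9.1.15.7 does not say that the CI50 aim applies to the summed plan.

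**The case against.** The best defence is that the waiver and its reason form one sentence. The reason concerns bone and nodal targets and the conclusion is only permissive, so Table 4, as the operative list, should govern a liver target. That is a sensible reading and may be the intended one. It is not written down, however. The conclusion is worded for the whole 20 Gy cohort, and the citation just before it concerns liver targets. A permission is enough to make two plans defensible.

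The second defence is size, and it stands. The bounds above are conservative because they use the 10 Gy volume for the 15 Gy volume. Interpolating geometrically between the protocol's aims of 1.6 (100% isodose) and 5 (50% isodose), which is a further assumption, gives about √(1.6 × 5) = 2.8 times PTV at 15 Gy. The threshold in a 1000 cc liver then becomes about 106 cc (5.9 cm). Against this, both indices are aims and not requirements.

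The third defence is existing safeguards: independent dose verification (9.1), dose-volume histograms for contoured organs (9.1.15.2), conventional radiotherapy where SABR is unsafe (9.1.3) and liver function tests at each cycle (Schedule of Events). These reduce the risk, but none says which liver rule to check against.

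Three stronger inferences are tempting, and the documents do not support them:

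- *The protocol orders liver targets to be planned without a limit.* It does not. The note only calls omission reasonable, and it argues from other sites.
- *Following the note also lifts the requirement in section 9.1.8 to image the whole liver.* It does not follow. The note relaxes a dose limit only; Table 4 still calls for the entire liver to be contoured, and section 9.1.15.2 still requires its histogram.
- *The trial's liver limit is printed backwards.* The oddly directed inequality is in a reported recommendation, and a misprint or a text-extraction error cannot be excluded. The direction of the Table 4 row, and whether it means entire or normal liver, need a source that is not available here.

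**Conclusion.** The inconsistency is real: an unqualified limit and a permission to omit it stand in the same section, the permission literally covers liver targets, and nothing ranks the two. It is a gap in scope and precedence, not evidence that the investigators mean to treat liver lesions without a limit.

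The consequence is confined to treatment planning and safety in patients with large or several liver targets, a number that the documents do not give. For a single target, the 60 cc threshold depends on the CI50 aim being met and on the assumed 1000 cc liver; from 1500 to 2000 cc it is 140 cc if both readings of the row are to be satisfied. For targets remote from the liver the two rules give the same plan. Sample size, analysis populations and every planned estimate are unaffected.

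**What to change.** In section 9.1.14:

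1. State that the Table 4 liver row applies to every plan with a liver or liver-adjacent target.
2. Restrict the waiver in the liver note to bone and lymph node targets away from the liver.
3. In the same edit, have the investigators confirm from their source whether the row means at least 700 cc of liver at ≤15 Gy or at most 700 cc above it, and write the direction out. Neither reading is stricter at every liver volume, so it should not be guessed.

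The cost is a few words of protocol text. Where the limit binds, a plan may lose some coverage, which section 9.1 already accepts down to D95=100%, or that lesion may move to conventional radiotherapy under section 9.1.3.
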